11.2. Deaths

Deaths during treatment (defined as deaths from the day of first dosing to 28 days after the last dose of study medication) and during the follow-up will be summarized by frequency of occurrence and corresponding percentage by cause of death per period (during treatment or follow-up) as well as overall. Listings of all deaths will be provided.

11.3. Second Primary Malignancy

Second primary malignancies are any occurring regardless of relationship to study drug during the conduct of the study including up to 5 years after last subject first dose date.

Events of SPMs will be tabulated for the following categories:

- All SPMs (invasive and non-invasive SPMs)
- All invasive SPMs (hematologic and solid tumor SPMs)
- All hematologic SPMs (AML, myelodysplastic syndromes (MDS), MDS to AML (for MDS events that transform to AML), B-cell malignancies, and other hematologic cancers)
- All solid tumor SPMs
- All non-invasive SPMs (non-melanoma skin cancers)

For each of the above SPM categories, SPMs will be further tabulated using the MedDRA preferred term. Each subject is counted only once within each SPM category as well as within each preferred term.

Additionally, the number and percentage of subjects with SPMs who died and those who did not die will be tabulated by SPM category.

It should be noted that these analyses with regard to SPMs are based on the number of subjects with at least one SPM and not the total number of SPMs.

For each SPM category, time to onset will be calculated as time (in months) from the start of the study treatment to the onset of the SPM for each affected subject. For the subjects with more than one new malignancy within an SPM category, the onset of the earliest SPM will be used. Time to onset will be summarized descriptively for each SPM category [mean, median, Standard Deviation (StdDev), first quartile (Q1), third quartile (Q3), minimum (Min), and maximum (Max)].

A scatter plot to graphically display the time to onset of hematologic and solid tumor SPMs for each SPM by dose level will be provided.

For each SPM category, the incidence rate per 100 person-years will be calculated as: (the number of subjects with any SPM in the SPM category/total person-years)*100. Total person-years are defined as the total time from the date of first treatment to the first onset date of the specified SPM for subjects with the specified SPM plus the total time from the date of first treatment to the date of the last follow-up or death for subjects without the specified SPM. Incidence rates per 100 person-years and the 95% confidence intervals will be calculated for each treatment arm and SPM category. Confidence interval at 95% level for the incidence rate per 100 person-years is calculated as follows: $\text{incidence rate} * \exp\{\pm 1.96 * n^{(-1/2)}\}$.

Listings for “Second Primary Malignancies” and for “Second Primary Malignancies Procedures for Cancers Not Under Study” will be produced by Celgene.

11.4. Clinical Laboratory Evaluations

Clinical laboratory values from the local laboratories will be graded according to NCI CTCAE version 4.03 for applicable tests using computerized programs. Frequency distributions for shift from baseline to the worst grade during treatment period will be presented.

Local lab results will be converted to standard units by a programmer using standard conversion factors and then each standardized result will be compared to literature reference ranges according to the age of the subject in order to compute the abnormality flags. Laboratory normal ranges from literature were provided by the Sponsor and can be found in Section 18.5.

Listings of clinical laboratory data from local laboratory with abnormal flags (H=High, L=Low) will be provided by subject and by parameter.

Both original and standardized results will be listed.

11.4.1. Hematology

Hematology testing including red blood cell (RBC) count, hemoglobin, hematocrit, mean corpuscular volume (MCV), WBC count and manual differential count (including blasts %, immature myeloid, absolute monocyte count, absolute neutrophil count (ANC)), and platelet count will be evaluated by the local laboratory at screening, on Days 1, 8, 15, and 22 of Cycles 1 and 2, on Day 1 of every cycle thereafter, at the Treatment Discontinuation Visit, on the 28-day Follow-up Visit, and at unscheduled visits.

White blood cell count, absolute blasts, absolute neutrophils and platelets will be recorded in the eCRF and results for all other hematology laboratory assay will not be collected on the eCRF but, instead, laboratory abnormalities that are considered AEs will be reported as AEs on the AE eCRF page.

The number and percentage of subjects with each NCI CTCAE grade will be presented for the parameters where grade will be assigned using computerized programs. A shift table representing the shift from the baseline grade to the worst grade (i.e. any time after first dose of study drug) will be provided for the safety population.

All collected hematology parameters will be presented in a listing for the ITT population.

11.4.2. Chemistry Laboratory Assessments

Serum chemistries including sodium, potassium, chloride, bicarbonate, calcium, phosphorus, blood urea nitrogen (BUN), creatinine, glucose, albumin, total protein, alkaline phosphatase, total bilirubin, direct bilirubin, aspartate aminotransferase (AST), alanine aminotransferase (ALT), and lactate dehydrogenase (LDH), and uric acid will be evaluated by the local laboratory at screening, on Days 1, 2, 4, 8, 15, and 22 of Cycle 1, on Days 1, 8, 15, and 22 of Cycle 2, on Day 1 of every cycle thereafter, at the Treatment Discontinuation Visit, on the 28-day Follow-up Visit, and at unscheduled visits. Serum chemistry laboratory values will not be collected on a laboratory eCRF; instead, laboratory abnormalities that are considered AEs should be reported on the AE eCRF page. No descriptive analysis of the chemistry laboratory results will thus be provided.

11.4.3. Urinalysis (dipstick)

No report will be provided for urinalysis.

11.5. Vital Signs

Vital signs (including sitting blood pressure, heart rate, respiration, and temperature) will be measured at screening, on Days 1, 8, 15, and 22 of Cycle 1, bi-weekly during Cycle 2, on Day 1 of every cycle thereafter, at the Treatment Discontinuation Visit, on the 28-day Follow-up Visit. At unscheduled visits vital signs will be measured. Height will be collected only at screening and on Cycle 1 Day 1. However, weight will be collected at screening and Day 1 of every cycle for dose adjustment.

Baseline is defined as the latest value collected on or before the date when the first dose of study treatment is administered. If multiple values are present for the same date, the mean of these values will be used as the baseline.

Summary statistics (n, mean, median, StdDev, Q1, Q3, Min, and (Max) of observed and change from baseline values will be presented.

Shift from baseline to worst value during the treatment (most extreme post-baseline value, where most extreme includes low and high category) will be displayed in cross-tabulations. For each vital sign parameter, the baseline grade and the worst grade post-baseline will be determined for each subject classified in below, within, and above the normal ranges. This table may include subjects with both normal and missing results for the vital sign, provided no abnormal (low or high) results will be reported. Low and high categories will be presented separately. In Table 3 normal ranges are reported.

Table 3 Normal Ranges of Vital Sign Measurements

Test	Age group ¹	Normal Range (Unit)
Diastolic Blood Pressure (DBP)	<2	[34,66] (mmHg)
	2-5	[34,74] (mmHg)

Test	Age group ¹	Normal Range (Unit)
	6-8	[35,80] (mmHg)
	9-13	[37,87] (mmHg)
	14-16	[40,91] (mmHg)
	≥17	[40,89] (mmHg)
Systolic Blood Pressure (SBP)	<2	[58,112] (mmHg)
	2-5	[60,125] (mmHg)
	6-8	[65,131] (mmHg)
	9-13	[68,141] (mmHg)
	14-16	[76,153] (mmHg)
	≥17	[70,139] (mmHg)
Pulse Rate	1-2	[95, 178] (bpm)
	3-7	[62, 124] (bpm)
	8-15	[48, 110] (bpm)
	≥16	[60, 100] (bpm)
Temperature	All	[35, 38] (°C) [95, 100.4.] (F)
Respiratory Rate	1-3	[24,50] (BPM)
	4-6	[22,34] (BPM)
	7-12	[18,30] (BPM)
	13-21	[12,16] (BPM)

1- Years reached at the time of the assessment.

Listings will be provided for all vital sign parameters for the ITT population.

11.6. Rates of acute and chronic graft-versus-host disease (GVHD)

Graft-versus-host disease (GVHD) will be summarized as collected in the “Adverse Events” eCRF page with the following preferred terms: “Acute graft versus host disease”, “Chronic graft versus host disease” and “Overlap syndrome”.

The incidence of GVHD TEAEs will be summarized by maximum CTCAE grade (1 or 2, higher than 2) within type of GVHD (overall, overlap, acute, chronic and overlap + acute GVHD).

Safety population subjects that had previous transplant (as collected in the “Stem Cell Transplants” eCRF page) will be selected for these summary tables and their total number will be used as denominator for the computation of incidence rates.

GVHD data as collected in the “GVHD” eCRF page will also be listed.

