7.2. Inclusion Criteria

Subjects must satisfy the following criteria to be enrolled in the study:

1. Male or female is 1 to ≤ 18 years of age at the time of signing the ICF/IAF.
2. Subject (when applicable, parental/legal representative) must understand and voluntarily provide permission to the ICF/IAF prior to conducting any study-related assessments/procedures.
3. Subject has rrAML after at least 2 prior induction attempts:
 - Bone marrow aspirate or biopsy must have $\geq 5\%$ blasts by morphology and/or flow cytometry.
 - Each block of chemotherapy (ie, ADE, MA) is a separate reinduction attempt.
 - Donor lymphocyte infusion (DLI) is considered a reinduction attempt.
4. Subject is willing and able to adhere to the study visit schedule and other protocol requirements.
5. Subject has a Karnofsky score of $\geq 50\%$ (subjects ≥ 16 years of age) or a Lansky score $\geq 50\%$ (subjects < 16 years of age).
6. Subject has a resting left ventricular ejection fraction (LVEF) of $\geq 40\%$ obtained by echocardiography.
7. Subject has recovered from the acute toxic effects of all prior chemotherapy, immunotherapy, or radiotherapy prior to first dose. All prior treatment-related toxicities must have resolved to \leq Grade 2 prior to enrollment.
8. Regarding radiation therapy, time elapsed prior to first dose of lenalidomide:
 - 2 weeks for local palliative radiation therapy (XRT).
 - 8 weeks if prior craniospinal chemoradiation therapy (CRT) or if $\geq 50\%$ radiation of pelvis.
 - 6 weeks if other bone marrow radiation has been administered.

9. Graft-versus-host disease criteria:

- Subject must be at least 2 months (from first dose of lenalidomide) from stem cell infusion.
- Subject must have no evidence of active acute or chronic GVHD (Grade 0) for 4 weeks prior to the first dose of lenalidomide.
 - If the subject has a history of maximum Grade 1 or 2 GVHD that was treated with systemic steroid (≥ 0.5 mg/kg/day prednisone equivalents) or other non-steroid systemic IST, the subject must be off all IST for at least 2 weeks, and must have ceased treatment doses of steroids for GVHD (≥ 0.5 mg/kg/day prednisone equivalents) for at least 4 weeks.
 - If the subject has a history of Grade 3 or greater GVHD, the subject must be off all systemic IST for 4 weeks.
 - Topical therapy is permitted and does not imply the subject has active acute or chronic GVHD.
- Physiologic dosing of hydrocortisone is permitted.

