10.9.1. Stopping Criteria for Acute Graft-Versus-Host Disease

Subjects who are post-allogeneic HSCT will be monitored closely for the development of acute graft-versus-host disease (GVHD). While Grade 1 to 2 GVHD will be tolerated, if 40% or more of subjects develop Grade 3 or higher GVHD, lenalidomide at this dose will be deemed intolerable for subjects who are post-HSCT.

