3.2. Secondary Objectives

The secondary objectives of the study are:

- To evaluate subject demographics and leukemic blast characteristics and their correlation with response to lenalidomide.
- To further evaluate lenalidomide activity with regards to response assessment outcome rates, transplantation rate and durable response rate.
- To evaluate the safety of lenalidomide including rates of graft-versus-host disease (GVHD) flare and reactivation.
- To determine the pharmacokinetics (PK) of lenalidomide in plasma.

[REDACTED]

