4.2.2. Secondary Endpoints

The secondary endpoints of the study are the following:

- Time to response.
- Durable response rate based on the revised AML IWG Criteria ([Cheson, 2003](#), see Section 18.1).
- Disease assessment outcomes and overall response rate (ORR).
- Rate of hematopoietic stem cell transplant (HSCT).
- Incidence and severity of treatment-emergent adverse events (TEAEs).
- Rates of acute and chronic graft-versus-host disease (GVHD).
- Plasma pharmacokinetic (PK) parameters including lenalidomide apparent clearance and volume of distribution.
- Correlation of peripheral white blood cell count, absolute blast count and cytogenetics with response to lenalidomide.

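### Both documents set an objective of GVHD flare and reactivation rates, but no such rate is defined or planned, and the pooled table in SAP 11.6 cannot supply one on its own

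*SAP*

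**What the plan says.** The SAP's secondary objective (3.2) is "To evaluate the safety of lenalidomide including rates of graft-versus-host disease (GVHD) flare and reactivation". Protocol 2.2 has the same objective. The matching endpoint in SAP 4.2.2 (and Protocol 3.2) is "Rates of acute and chronic graft-versus-host disease (GVHD"), with no mention of flare, reactivation or new onset.

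SAP 11.6 states the breakdown: "The incidence of GVHD TEAEs will be summarized by maximum CTCAE grade (1 or 2, higher than 2) within type of GVHD". The types are overall, overlap, acute, chronic, and overlap plus acute. The population is "Safety population subjects that had previous transplant", and "their total number will be used as denominator for the computation of incidence rates". The GVHD "eCRF page will also be listed", but no rate is derived from that page.

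On entry status, Protocol 7.2 criterion 9 says: "Subject must have no evidence of active acute or chronic GVHD (Grade 0) for 4 weeks prior to the first dose of lenalidomide". The same criterion admits subjects with earlier GVHD and sets different immunosuppression-free periods by its grade and treatment.

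**The concern.** In ordinary use, flare and reactivation describe GVHD that returns or worsens in someone who has had it. The planned table does not identify those subjects. A child whose GVHD recurs on lenalidomide and a child who develops it for the first time fall in the same cell, over the same denominator.

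The protocol treats the distinction as important. Section 1.4.2 and criterion 9 handle subjects with a severe or treated GVHD history differently from the rest. A reader of the report would want to know how often GVHD came back in that group, and the plan produces no such figure.

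A smaller point concerns transplant type. Protocol 10.9.1 places the risk after allogeneic HSCT, while SAP 11.6 asks only for a previous transplant.

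**Working it through.** **The only GVHD figure in the documents.** Protocol 10.9.2 stops enrolment of post-HSCT subjects at 4 or more Grade 3–4 cases in the first 15, with null rate 0.10, alternative 0.40, alpha 0.10 and power 90%. Using P(X ≥ 4) = Σ C(15,k) p^k (1−p)^(15−k) for k = 4 to 15:

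- p = 0.10 gives 0.056, within the 0.10 ceiling.
- p = 0.40 gives 0.909, matching the stated 90%.
- A threshold of 3 would give a type I error of 0.184; a threshold of 5 would give power of 0.783.

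The rule is sound and the present point does not depend on it.

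**Does any planned output give a flare or reactivation rate?**

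| Output | Separates recurrence from new onset? |
|---|---|
| SAP 11.6 table | No. Grade within type, one denominator |
| SAP 11.1.3 shift tables (GVHD is a listed category) | No. Criterion 9 puts eligible subjects at Grade 0, so those with and without a history share one baseline |
| SAP 11.6 listing of the GVHD eCRF page | Possibly at subject level; the page content is not shown, and no rate is planned |
| SAP 8.1.3 medical history summary and listing (up to 5 years) | Possibly at subject level; not linked to on-study GVHD |

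The visible text of SAP 16, which lists changed and dropped analyses, does not withdraw the objective.

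**Can the pooled rate stand in for the missing one?** Let s be the share with earlier GVHD, a the GVHD rate in that group and b the rate in the others. Then pooled = s·a + (1 − s)·b. The documents give none of these, so the values are assumed:

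| s | a = 40%, b = 10% | a = 10%, b = 40% |
|---|---|---|
| 20% | 0.2×0.4 + 0.8×0.1 = 16% | 0.2×0.1 + 0.8×0.4 = 34% |
| 40% | 0.4×0.4 + 0.6×0.1 = 22% | 0.4×0.1 + 0.6×0.4 = 28% |
| 60% | 0.6×0.4 + 0.4×0.1 = 28% | 0.6×0.1 + 0.4×0.4 = 22% |

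A pooled 22% arises when the rate with a history is 40% (s = 40%) and also when it is 10% (s = 60%). The same holds for 28%. The pooled figure does not identify a, and it can err in either direction.

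**In counts.** Assume 15 post-transplant subjects, 6 with earlier GVHD, and 3 GVHD cases in all. Intervals are Clopper-Pearson 95%.

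| | Cases | Interval |
|---|---|---|
| Pooled | 3/15 = 20% | 4% to 48% |
| All recurrences: history / no history | 3/6 = 50% / 0/9 = 0% | 12% to 88% / 0% to 34% |
| All new onset: history / no history | 0/6 = 0% / 3/9 = 33% | 0% to 46% / 7% to 70% |

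The same table entry is compatible with recurrence rates from 0% to 50%.

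**The case against.** The strongest defence is that SAP 11.6 delivers the prespecified endpoint exactly. It carries that endpoint's name and reports it by type and grade. This stands: the mismatch lies between objective and endpoint and begins in the protocol, so rewording the objective would also close it.

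A reader might infer that flare and reactivation rates cannot be reported at all. The documents do not support that. The GVHD listing, the medical history listing and the eligibility data may allow a later derivation. What can be said is that none is defined or planned.

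A reader might also infer that the pooled rate is diluted and so understates the risk with prior GVHD. That assumes recurrence is more frequent than new onset, which nothing in the documents shows. Nor do they say whether any subject had only an autologous transplant, so distortion from that source is speculative. Stating allogeneic simply aligns the table with Protocol 10.9.1.

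It is tempting to call every on-study case in a subject with a history a recurrence. That fails for a first chronic GVHD after resolved acute GVHD, for history from an earlier graft in a re-transplanted subject, and for GVHD after a new transplant within the 28-day window for treatment-emergent events. Criterion 9 does not capture every history either: its conditions name systemically treated Grade 1–2 and Grade 3 or greater.

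Finally, flare and reactivation are undefined in the visible text, parts of which are redacted, and the subgroups will be small. Both limit what a split table can show. Neither gives the stated objective an analysis.

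**Conclusion.** The point holds in this form: both documents state an objective of GVHD flare and reactivation rates, no planned summary in the visible text produces one, and the pooled table alone cannot supply it. Its numerical size cannot be given. The illustrations rest on assumed shares, rates and counts, and show only that the pooled rate may lie on either side of the rate in subjects with prior GVHD.

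The conclusion takes flare and reactivation in their ordinary sense and rests on the visible text. It does not touch the primary endpoint, the two-stage rule or the GVHD stopping rule. It goes beyond missing detail, because following the plan exactly would leave a stated safety objective unanswered when a split of an existing table could answer it.

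**What to change.** In SAP 11.6:

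1. Restrict the denominator to safety-population subjects with a prior allogeneic HSCT.
2. Define flare/reactivation as a treatment-emergent GVHD event in a subject with GVHD recorded before first dose, using the GVHD, medical history or eligibility data. Define new onset as such an event in a subject without recorded GVHD.
3. Tabulate each by type and grade, with its own denominator and Clopper-Pearson 95% interval.
4. Show separately a first chronic GVHD after earlier acute GVHD, cases where the history belongs to an earlier graft in a re-transplanted subject, and GVHD after an on-study transplant.
5. Give unknown history its own row.

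If the history data prove inadequate, reword the objective in Protocol 2.2 and SAP 3.2 to match the endpoint.

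The cost is a few definitions and one split of a planned table, drawing on history that eligibility already requires in part. The sponsor should first confirm what the GVHD eCRF page records. The downside is small subgroups with wide intervals, so the results should be presented as descriptive only.

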11.7. Karnofsky or Lansky Performance Status Score

Performance status will be measured using either the Karnofsky or Lansky performance status score (Karnofsky performance status score for subjects ≥ 16 years of age or Lansky performance status score for subjects < 16 years of age) at screening, on Day 1 of each cycle and at the Treatment Discontinuation Visit. For performance status scores, shift from baseline to worst value and best score during the treatment period will be displayed for the whole treatment period and by cycle. Subjects changing age category during the study, ie, having both performance status results, will be included into the summary statistics computation.

Performance status scores will also be presented in a listing for the ITT population.

11.8. Other Safety Assessments

Data collected for other safety assessments including pregnancy status, chest x-ray, electrocardiogram and echocardiography will be listed.

Summary of pregnancy status will be provided for females of childbearing potential.

[REDACTED]

CEL GENE PROPRIETARY INFORMATION

13. PHARMACOKINETIC (PK) ANALYSES

13.1. Pharmacokinetics

13.1.1. Handling of Pharmacokinetic Data

Concentrations that are below the limit of quantitation (BLQ) prior to the first dose will be assigned a numerical value of zero. Post-treatment concentrations that are BLQ will be treated as missing. Concentrations assigned a value of missing will be omitted from the descriptive statistics. A concentration value of zero will be excluded from the computation of the geometric mean (geometric CV%). Geometric CV(%) is calculated as follows: $CV(\%) = 100 \times \sqrt{\frac{V}{(\bar{V})^2}}$, where V denotes the variance of the log-transformed values.

If any subjects are found to be noncompliant with respect to dosing, have incomplete data, or encounter other circumstances that would affect the evaluation of pharmacokinetics, a decision will be made on a case-by-case basis as to their inclusion in the PK analysis. Data excluded from pharmacokinetic analysis will be included in the data listings, but not in the summaries.

In tables and listings for the derived PK data, there should be four decimal places for numerical values below 1, three decimal places for numeric values below 10 but above 1, and two decimal places for numeric values above 10. However, the listings of raw data should not have more or fewer decimal places than the actual data.

13.1.2. Pharmacokinetic Parameters

Pharmacokinetic parameters of lenalidomide will be calculated from concentration-time profiles using non-compartmental methods, though compartmental analysis may be employed if appropriate. Pharmacokinetic parameters will include, but not be limited to:

- C_{max} : observed maximum plasma concentration
- T_{max} : observed time to maximum plasma concentration
- AUC_t : area under the plasma concentration-time curve from time zero to the last quantifiable timepoint, calculated by the linear trapezoidal rule
- AUC_{24} : area under the plasma concentration-time curve from time zero to 24 hours postdose calculated by the linear trapezoidal rule
- AUC_{∞} : area under the plasma concentration-time curve from time zero to infinity, calculated by the linear trapezoidal rule and extrapolated to infinity will be calculated according to the following equation:
 $AUC_{\infty} = AUC_t + (C_t/\lambda_z)$, where C_t is the last quantifiable concentration.
- λ_z : terminal phase rate constant, determined by linear regression of the terminal points of the log-linear plasma concentration-time curve. Visual assessment may be used to identify the terminal linear phase of the log concentration-time profile. A minimum of 3 data points will be used for the calculation. The λ_z will not be

estimated if the terminal phase of the log-concentration-time profile does not exhibit a linear decline phase, or if the regression coefficient (Rsq) is less than 0.8

- $t_{1/2}$: terminal phase half-life, calculated as $t_{1/2} = [0.693/\lambda_z]$
- CL/F: apparent total clearance when dosed orally, calculated as $[Dose/AUC_{\infty}]$
- Vz/F: apparent volume of distribution when dosed orally, calculated as: $V_z = [CL/\lambda_z]$

The following plasma PK parameters will be calculated for diagnostic purposes summarized and listed,

- λ_z lower: lower limit of time (h) included in the calculation of λ_z
- λ_z upper: upper limit of time (h) included in the calculation of λ_z
- λ_z N: number of data points used in the calculation of λ_z
- Rsq: regression coefficient for calculation of λ_z
- AUC %extrap: percentage of AUC_{∞} due to extrapolation from the time for the last quantifiable concentration to infinity, calculated as $(AUC_{\infty}-AUC_t)/AUC_{\infty}*100$

The PK parameters shown above will be calculated from samples collected on Day 1 as described in section 18.2.1. Additional parameters may also be calculated. Actual blood draw times relative to dosing will be used for all plasma PK parameters computations.

Only subjects included in the PK population shall be considered for PK analysis.

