1.3.2. Lenalidomide Pharmacokinetics

1.3.2.1. Pharmacokinetics in Pediatric Populations

The pharmacokinetics (PK) of lenalidomide have been evaluated in pediatric patients with solid tumors in two Phase 1 pediatric studies (Berg, 2011; Warren, 2011). A total of 47 pediatric patients were evaluated for PK in the two studies, with ages ranging from 4 to 21 years old. Doses studied were 20 to 116 mg/m²/day for children with brain tumors, 15 to 70 mg/m²/day for children with solid tumors, and 5 mg/m²/day for children with MDS. In these pediatric patients, plasma lenalidomide exposure (AUC and C_{max}) increased approximately proportional to dose. The median time to reach the maximum concentration in plasma was approximately 1 to 4 hours following the oral administration and the mean terminal half-life (t_{1/2}) of lenalidomide was 2 to 3 hour in the two studies. These observations are consistent with those historically observed in adult patients with hematological malignancies including AML.

In pediatric patients ≥ 5 years of age, preliminary population PK analysis suggests that body weight is positively correlated with lenalidomide clearance and volume of distribution, but age has no effect.

The relationship between lenalidomide apparent total clearance (CL/F) and body size (weight or body surface area [BSA]) is not available for children younger than 5 years. Because gastrointestinal (GI) and renal functions reach the adult level by 1 year of age, oral absorption and renal elimination of lenalidomide is not anticipated to be highly age-dependent in patients 1 to 5 years. However, effects of the growth-dependent changes in the body size on lenalidomide clearance (plasma exposure) and volume distribution is expected in the 1 to < 5 year-old age group of pediatric patients. The impact of growth on plasma lenalidomide exposure has been taken into account when considering the weight-based dose for this study.

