18.2. Pharmacokinetic Sample Collection

18.2.1. Blood Collection for PK Analysis

Collection of blood samples for PK assessments in plasma will be performed in all subjects. On Cycle 1 Day 1, the subjects will receive the dose of lenalidomide in the morning at the study center. Subjects will undergo PK sampling of blood at scheduled time points (Table 5) for 24 hours post-dose. The actual date and time for dosing and blood sampling should be recorded in the eCRF.

Table 5: PK Sampling Schedule During Cycle 1 Day 1

Collection time after lenalidomide administration ^a	Collection window	Weight ≤ 20 kg ^b	Weight > 20 kg ^c
0.5 hour	± 10 min	-	x
1 hour	± 10 min	x	x
2 hours	± 10 min	x	x
4 hours	± 10 min	x	x
6 hours	± 10 min	-	x
8 hours	± 10 min	x	x
24 hours*	± 2 hours	x	x

PK = pharmacokinetic.

* The 24 hour blood sample must be taken prior to the lenalidomide administration on Day 2.

^a The blood draw volume is 1 mL per sample.

^b Only 5 PK blood samples will be taken from subjects with weight ≤ 20 kg at the specified time points.

^c Seven PK blood samples will be taken from subjects with weight > 20 kg.

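### The linear trapezoid across the unsampled 8 to 24 h gap gives CL/F and Vz/F a bias that switches with whether the 24 h sample is quantifiable

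*SAP*

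**What the plan says.** SAP 13.1.2 defines AUCt as "area under the plasma concentration-time curve from time zero to the last quantifiable timepoint, calculated by the linear trapezoidal rule", and AUC24 and AUC-infinity are likewise "calculated by the linear trapezoidal rule"; no log rule is given for the declining phase. AUC-infinity is AUCt + Ct/λz, where Ct "is the last quantifiable concentration". For λz, "A minimum of 3 data points will be used for the calculation", and it is not estimated if Rsq is below 0.8. CL/F is the "apparent total clearance when dosed orally, calculated as" Dose/AUC-infinity, and Vz/F divides that by λz. SAP 13.1.1 adds: "Post-treatment concentrations that are BLQ will be treated as missing".

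The schedule in SAP 18.2.1 is 0.5, 1, 2, 4, 6, 8 and 24 h above 20 kg. For the lighter children, "Only 5 PK blood samples will be taken from subjects with weight" of 20 kg or less, at 1, 2, 4, 8 and 24 h. Protocol 1.3.2.1 reports that the mean terminal half-life "was 2 to 3 hour in the two studies".

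Apparent clearance and volume of distribution are a secondary endpoint (Protocol 3.2, SAP 4.2.2), summarised by age class (SAP 13.1.3).

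**The concern.** After absorption the concentration falls roughly exponentially, and a straight line drawn over many half-lives lies well above such a curve. The 8 to 24 h interval is 16 h long, which is 16/3 = 5.3 to 16/2 = 8 half-lives. If the 24 h sample is quantifiable, the whole excess enters AUCt. If it is BLQ, AUCt stops at 8 h, the tail becomes C8/λz, and the excess is gone. Which of two estimators a child receives therefore depends on a limit of quantitation that the documents do not state.

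At stake is the accuracy of a named secondary endpoint. SAP section 16 lists population PK among the analyses not to be conducted, while SAP 13.1.4 assigns it to a separate report. If it is not done, these non-compartmental values are the planned source for CL/F and Vz/F, unless the optional compartmental analysis is used.

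**Working it through.** The plan states no AUC error or CL/F precision, so there is no figure to reproduce.

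**Inputs.** Sampling times and AUC, λz and BLQ rules from SAP 13.1.1, 13.1.2 and 18.2.1; half-life 2 to 3 h from Protocol 1.3.2.1. Assumed: one-compartment oral model without noise, absorption rate ka 1 to 4 per h, λz from the last three quantifiable points.

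**Formulas.** C(t) = A·ke·ka/(ka − ke)·(exp(−ke·t) − exp(−ka·t)), with ke = ln 2/half-life and true AUC A = 100, so results read as percentages.
- Linear segment: Δt·(C1 + C2)/2.
- Log segment: Δt·(C1 − C2)/ln(C1/C2).

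**Worked case: half-life 2.5 h, ka 2 per h, above 20 kg.** ke = 0.6931/2.5 = 0.2773 per h. C8 = 3.503 and C24 = 0.0415.
- Linear area 0 to 8 h: 4.045 + 9.054 + 18.968 + 28.505 + 16.706 + 9.601 = 86.88.
- Linear area 8 to 24 h: 16 × (3.503 + 0.0415)/2 = 28.35. The true area is 12.48.
- 24 h quantifiable: 86.88 + 28.35 + 0.0415/0.2773 = 115.38, error +15.4%. CL/F ratio 100/115.38 = 0.867, so 13.3% too low.
- 24 h BLQ: 86.88 + 3.503/0.2770 = 99.52, error −0.5%.
- Log rule on 8 to 24 h only: 16 × (3.503 − 0.0415)/ln(3.503/0.0415) = 12.48, total 99.51, error −0.5%.
- Full linear-up/log-down: −1.8% with the 24 h value quantifiable or BLQ.

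The percentage extrapolated is 0.15/115.38 = 0.13% in the biased case and 12.6/99.52 = 12.7% in the nearly unbiased one, so this diagnostic points the wrong way.

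**Grid: half-life 2, 2.5, 3 h by ka 1, 2, 4 per h. Error in AUC-infinity.**

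| Rule and 24 h result | Above 20 kg | 20 kg or less |
|---|---|---|
| Linear, quantifiable | +11.3% to +17.8% | +6.9% to +18.3% |
| Linear, BLQ | −1.0% to 0.0% | −5.4% to +2.8% |
| Log on 8–24 h only, quantifiable | −1.0% to −0.2% | −5.4% to 0.0% |
| Linear-up/log-down, quantifiable | −3.0% to −1.5% | −9.8% to −3.0% |
| Linear-up/log-down, BLQ | −3.0% to −0.6% | −9.8% to +0.8% |

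With a BLQ 24 h sample, log on 8–24 h only is the same as the linear rule. The quantifiable-to-BLQ step under the linear rule is 12 to 18 points. For CL/F, 1/1.069 = 0.935 and 1/1.183 = 0.845, so about 6% to 16% too low.

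**Check against Protocol Table 1.** Matching its AUC and Cmax with Tmax 1 h gives a half-life of 1.94 h (1 to < 2 years) and 2.60 h (12–18 years).
- 1 to < 2 years: C8 74.2, C24 0.242 ng/mL. Linear 8 to 24 h area 8 × 74.4 = about 596 against a true 207 h·ng/mL. AUC-infinity error +11.0% quantifiable, −1.8% BLQ.
- 12–18 years: C8 211.9, C24 2.987 ng/mL. Linear area 8 × 214.9 = 1719 against a true 784. Error +15.1% quantifiable, −0.5% BLQ.

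Fixing Tmax at 2 h raises the largest error to about +20%. Over half-lives of 2 to 3 h and Tmax 1 to 2 h, predicted C24 is about 0.24 to 7.2 ng/mL, so an ordinary difference in assay limit could decide which estimator applies.

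**The case against.** **Clearance still tracks the child.** A reader might infer that CL/F would reflect the assay instead of the child. That is not supported. In a simulation (5,000 children per age group, CV about 26% for CL/F and 20% for V/F, assumed limit 0.5 to 10 ng/mL), estimated and true log CL/F correlate at 0.98 to 0.99. Whether the 24 h sample is quantifiable depends partly on the child's own clearance, half-life and dose. Nor would two children with identical profiles under one assay get different answers, since they share the same 24 h status. The step separates children on either side of the limit, or the same profile under two assays.

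**The age contrast is not the linear rule's alone.** A reader might also blame that rule for a false difference between age groups. In the same simulation the ratio of estimated to true CL/F is 0.99 to 1.04 (1 to < 2 years) against 0.90 to 0.98 (12–18 years). Under log-down it is 1.10 against 1.02. The contrast hardly changes, because the two weight schedules differ in their early samples.

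**Log-down has a cost.** On the 5-sample schedule with a BLQ 24 h value, half-life 2 h and ka 2, the linear error is −1.4% and log-down −6.0%; at ka 4 they are −5.4% and −9.8%. The simulation puts 62% to 97% of the youngest group at BLQ, where the linear rule is usually closer to the truth. This stands. The quantifiable-to-BLQ step also does not vanish there under log-down: it reaches 3.8 points at half-life 3 h and ka 1.

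**Low stakes.** All analyses are descriptive (Protocol 10.1), no PK result drives a decision, and Protocol 10.10 puts population PK first with non-compartmental values optional. This limits the weight of the point, but SAP section 16 leaves that fallback in doubt.

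**Conclusion.** The point holds as a correctable bias in a descriptive secondary endpoint. When the 24 h sample is quantifiable, the planned rule overstates AUC-infinity by about 7% to 18%, so CL/F, and Vz/F through it, come out about 6% to 16% too low. When the sample is BLQ, the AUC error lies within about −5% to +3%. The bias is smaller than the assumed between-child CV of about 26%, but it is systematic and invisible to the planned diagnostic.

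These sizes rest on a one-compartment, noise-free model with assumed absorption rates. How many children fall on each side cannot be known without the limit of quantitation. The documents support neither the reading that CL/F ceases to measure the child nor the reading that this rule alone creates an age difference.

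**What to change.** In SAP 13.1.2, replace the linear rule by linear-up/log-down for AUCt, AUC24 and AUC-infinity, or at minimum use the log rule for the 8 to 24 h interval. State how AUC24 is obtained when the 24 h sample is BLQ, which the SAP leaves open. Giving the limit of quantitation and the number of BLQ 24 h samples beside each CL/F summary would let a reader judge what remains.

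The cost is a few words and a software setting, with no new samples. The downside to record is that full log-down understates AUC by up to about 10% in children of 20 kg or less, because their early samples are sparse, so a difference between the two weight schedules remains. Applying the log rule only from 8 to 24 h gives smaller errors in most of the cases above, partly because the linear rule's excess on the early decline offsets what is missed around the peak. Either choice removes most of the switch; neither makes the estimate unbiased.
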